--	---

Immune Design**G100 (GLA-SE) and Pembrolizumab or Rituximab****Protocol IMDZ-G142; Version 04B, November 15, 2018**

	
Part 4 will consist of a Dose Escalation group to evaluate and establish the safety of injecting 20μg of G100 into multiple lesions (up to 4 lesions) in combination with pembrolizumab and a Patient Expansion group to assess clinical responses with this regimen. At least 22 relapsed or refractory follicular NHL patients who received ≥ 3 prior systemic therapies will be treated in Part 4. Twenty-two efficacy evaluable patients as defined in the Statistical Section will be enrolled.
 
During Dose Escalation, safety will be assessed using a 3+3 design where sequential cohorts of patients will be treated with intratumoral G100 at 20μg/lesion in 1, 2, 3, or 4 tumor lesions corresponding to systemic G100 exposure of 20, 40, 60 or 80μg G100. Once the 20 μg systemic dose level cohort (20 μg injected in 1 lesion) has been established to be reasonably safe, patients who do not qualify to enroll on the next dose level cohort due to insufficient numbers of potentially injectable lesions may enter Patient Expansion at that single lesion dose level. As each higher systemic dose level (40 μg, 60 μg, 80 μg) in multiple lesions is established to be well-tolerated, additional patients who otherwise qualify for the study but are unable to be treated on Dose Escalation due to insufficient numbers of injectable lesions will be allowed to enroll into the Patient Expansion portion of the study at the established safe dose levels. If complete enrollment of 22 efficacy evaluable patients is reached before Dose Escalation is complete, the Sponsor may choose to continue enrollment into just the Dose Escalation cohorts with up to 12 patients to fill all or some of the remaining cohort(s).
 
Treatment will follow a similar dose regimen as in "Part 2, Patient Expansion With or Without Pembrolizumab" group, except that radiation therapy has been omitted. G100 will be injected intratumorally beginning on Day 0, a second dose will be administered 5-7 days later (Study Day 5-7) and then dosing will continue weekly for up to 4 additional doses (6 total) as long as the tumor remains of sufficient size for injection. At least 1 lesion will be targeted to receive each dose of G100. If the lesion regresses, another lesion will be chosen for treatment (as described in the protocol). If the patient is entered in a cohort where more than one lesion is injected (cohorts 2 to 4), as many easily accessible tumors will be targeted and treated as specified for the cohort. Imaging assisted injections are allowed but the feasibility and safety of these treatments must be discussed first and approved by the Medical Monitor. If the tumor mass has not regressed completely from baseline, dosing may continue for 3 additional weekly intratumoral doses (9 total). On Day 14, pembrolizumab treatment will be initiated at a standard dose of 200 mg intravenously (IV) and then be administered every 3 weeks (q3W) IV for up to 2 years or until disease progression or unacceptable toxicity.
 
Part 4 Dose Escalation
 
In the Dose Escalation portion, safety will be assessed using a 3+3 design where 12 to 24 patients will be assigned to sequential cohorts of escalating

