Treatment will follow a similar dose regimen as in "Part 2, Patient Expansion With or Without Pembrolizumab" group, except that radiation therapy has been omitted. G100 will be injected intratumorally beginning on Day 0, a second dose will be administered 5-7 days later (Study Day 5-7) and then dosing will continue weekly for up to 4 additional doses (6 total) as long as the tumor remains of sufficient size for injection. At least 1 lesion will be targeted to receive each dose of G100. If the lesion regresses, inject around the area where the lesion was until the course is complete. If the patient is entered in a cohort where more than one lesion is injected (cohorts 2 to 4), as many easily accessible tumors will be targeted and treated as specified for the cohort. Imaging assisted injections are allowed but the feasibility and safety of these treatments must be discussed first and approved by the Medical Monitor. If the tumor mass has not regressed completely from baseline, dosing may continue for 3 additional weekly intratumoral doses (9 total). On Day 14, pembrolizumab treatment will be initiated at a standard dose of 200 mg intravenously (IV) and then be administered every 3 weeks (Q3W) IV for up to 2 years or until disease progression or unacceptable toxicity.

Immune Design

G100 (GLA-SE) and Pembrolizumab or Rituximab

Protocol IMDZ-G142; Version 04B; November 15, 2018

Part 4 Dose Escalation

In the Dose Escalation portion, safety will be assessed using a 3+3 design where 12 to 24 patients will be assigned to sequential cohorts of escalating number of G100 injected lesions in combination with standard dose pembrolizumab ([Figure 6](#)). Four cohorts are planned:

- Cohort 1: G100 20 µg/lesion in 1 tumor
- Cohort 2: G100 20 µg/lesion in 2 tumor lesions (40µg total)
- Cohort 3: G100 20 µg/lesion in 3 tumor lesions (60µg total)
- Cohort 4: G100 20 µg/lesion in 4 tumor lesions (80µg total)

Once a Cohort dose level is established to be safe, patients who do not meet the criteria of sufficient numbers of injectable tumors to enter the next dose Cohort will be enrolled in a Patient Expansion group at a systemic dose level that has already been established as safe.

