8.1.4 G100 Administration

For Parts 1, 2, or 3, patients with follicular NHL with at least one tumor mass that is being considered for radiation therapy that is also accessible and assessed to be safe for intratumoral injection are eligible for enrollment. In Part 4 and Part 5, similar patients are eligible for enrollment except that radiation therapy has been omitted. All patients must also have a second site where tumor response can be assessed. For example, the second untreated, abscopal site could be a measurable tumor lesion or involvement of skin. For Parts 4 and 5, the G100 treated site(s) and a non-injected site (unless not available and prior approval is provided by Medical Monitor) must be measurable (Index) lesions and be followed by imaging studies and recorded. Skin lesions and other lesions measured by exam are acceptable if lesions can be measured by reproducible methods and preferably if photographically documented.

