In the optional treatment group for Large Tumor patients, up to 4 patients with injectable lymphoma mass(es) 4 cm or greater in total size will be enrolled and receive G100 consisting of 20 µg of the GLA component per dose. In Part 3, G100 Expansion of 20 µg Dose Group, up to

Immune Design

G100 (GLA-SE) and Pembrolizumab or Rituximab

Protocol IMDZ-G142; Version 04B, November 15, 2018

25 patients will be enrolled and treated with 20 µg/dose. Treatment with G100 would be administered on the same treatment schedule as in Part 1 except that the dose would be higher (See [Figure 4](#)). Depending on the treatment volume, the dose should be administered to a single large target lesion or distributed among 2 or more lesions within the radiation field. If the target lesion(s) regresses, a different lesion(s) within the radiation field will be chosen for treatment, if available.

Parts 4 and 5: In Part 4, patients will be treated with G100 at 20 µg/lesion in combination with pembrolizumab, and the treatment schedule will follow that in [Figure 7](#). Overall, 22 efficacy evaluable patients as defined in the Statistical Section will be enrolled. In Part 5, 12-24 patients will be treated during Dose Escalation and 20 efficacy evaluable patients as defined in the Statistical Section will be enrolled following the treatment schedule in [Figure 9](#). For Parts 4 and 5, radiation therapy has been omitted. Once identified, easily accessible lesion(s) will be targeted to receive each dose of G100. If the initially injected lesion(s) regresses before completion of therapy, another site may be chosen for treatment. If the patient is entered in a cohort where more than one lesion is injected (Part 4, cohorts 2 to 4 or expansion group), as many easily accessible tumors will be targeted and treated as specified for the cohort treatment group. Imaging assisted injections are allowed but the feasibility and safety of these treatments must be discussed first and approved by the Medical Monitor.

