As much of the full dose as possible should be given and the total dose of G100 administered should be recorded for each administration. As noted above, it should be expected that there will be peritumoral administration of G100 from either direct or extravasation following injection. In Parts 1 to 4, if the tumor mass has not regressed completely following 6 doses, treatment may continue for 3 additional weekly intratumoral doses (9 total). At the discretion of the investigator, should the G100 treated lesion(s) become too small or inaccessible for injection, G100 therapy will stop and the patient will continue to be followed for tumor response at distal sites and for long-term clinical status. In Part 5, up to 6 doses will be administered.

For All Parts (1 to 5)

Retreatment / Second Course: Patients may be eligible to receive a second course of G100 if they achieved SD or better or have PD that does not require immediate therapy, have accessible and injectable lesions outside the prior radiation field, and have not had significant treatment emergent AEs (including events that would be considered a DLT) as determined by the investigator and the Sponsor. For patients enrolled on Parts 4 or 5, the same previously injected tumor sites may be targeted or a replacement site(s) may be chosen.

Six weeks or more after completion of the first course of G100 treatment, the second course would begin and consist of G100 alone (no radiation and no additional rituximab) at the same dose received during the first course of therapy. Treatment would be administered on a similar weekly schedule as the first course except without radiation therapy (or rituximab therapy). G100 will be injected intratumorally beginning on Day 0 (instead of Study Day 2), a second dose

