10.3.3 Visit 3 and Visit 4: Radiation Therapy (Day 0 and Day 1)

Patients receive local radiation therapy to tumor mass identified for intratumoral treatment. Standard 2Gy each day \times 2 is recommended. Treatment plan will be determined by the treating radiation therapist. Changes in doses should be discussed with Immune Design.

As part of this study, the injected lesion(s) is followed for local effect, and untreated, abscopal lesions are followed for systemic treatment effect. Therefore the G100 treated / irradiated lesion should be one of the Index (target) lesions followed for response. In addition, the radiation treatment field should be reviewed by the radiation therapist to confirm the identity of all irradiated lesions and untreated “abscopal” lesions to be used to follow treatment response. (For the purpose of this study, abscopal tumor site refers to a lesion that is not irradiated or injected / treated that can be followed for shrinkage that would indicate a systemic immune effect)

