10.3.17 Visit 4: G100 Dose #2 (Day 5-7)

Patients will return for the second dose of G100 on either Day 5, 6, or 7. Note that on each immunization day, all procedures and blood draws must be done before dosing. The following will be completed:

- 1) Review of AEs and SAEs
- 2) Recording of any previous / concomitant medications
- 3) Vital signs
- 4) Symptom-directed physical exam
- 5) Assessment and measurements of tumor treated with G100 and measureable untreated distal tumor lesions by exam
- 6) ECOG status
- 7) Safety labs as in [Section 10.3.2](#) – Hematology, Clinical chemistry
- 8) G100 administration

10.3.18 Visits 5, 6, 7, 8: G100 Doses #3, 4, 5, 6 (Days 14, 21, 28, 35)

Patients will return for their G100 doses #3, 4, 5, and 6. Note that on each immunization day, all procedures and blood draws must be done before dosing. The following will be completed:

- 1) Review of AEs and SAEs
- 2) Recording of any previous / concomitant medications
- 3) Vital signs
- 4) Symptom-directed physical exam
- 5) Assessment and measurements of tumor treated with G100 and measureable untreated distal tumor lesions by exam
- 6) ECOG status
- 7) Safety labs as in [Section 10.3.2](#)– Hematology, Clinical chemistry
- 8) Pharmacokinetics and Pharmacodynamic labs (Visit 5 Day 15 only)
- 9) G100 (20 µg/lesion) administration (Note: If the injected tumor(s) regressed and is no longer of sufficient size for injection (either intra- or peritumoral) per evaluation by the investigator and there are no easily accessible alternate lesions – i.e., There are no longer any injectable lesions, the remaining G100 treatments and G100 only treatment visits may be cancelled. The patient should then continue with pembrolizumab and Clinical Assessment visits)
- 10) Urine pregnancy test on Day 14 prior to pembrolizumab. Note: For patients in UK and France, urine pregnancy tests must also be performed every month or sooner while the patient is receiving G100 and/or pembrolizumab.
- 11) On Day 14 and 35, administer pembrolizumab

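### Part 4 gives conflicting current instructions for a regressed injected lesion, so which lesions remain abscopal depends on the section a site follows

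*Protocol*

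**What the plan says.** The Part 4 text in force covers a regressing injected lesion in several places.

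- Protocol 6.1 (Part 4): "If the lesion regresses, inject around the area where the lesion was until the course is complete". The same paragraph makes weekly dosing conditional: "as long as the tumor remains of sufficient size for injection".
- Protocol 3.1 (synopsis, Part 4), repeated in SAP 3.1: "If the lesion regresses, another lesion will be chosen for treatment (as described in the protocol").
- Protocol 8.1.4 (Parts 4 and 5): "If the initially injected lesion(s) regresses before completion of therapy, another site may be chosen for treatment".
- Protocol 8.1.4, slightly later and at the investigator's discretion: "should the G100 treated lesion(s) become too small or inaccessible for injection, G100 therapy will stop". Nothing there requires a search for another lesion first.
- Protocol 10.3.18 and 10.3.19 (Part 4 dosing visits): if neither intratumoral nor peritumoral injection is possible and no easily accessible alternate lesion exists, then "There are no longer any injectable lesions, the remaining G100 treatments and G100 only treatment visits may be cancelled".

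Two further passages fix what counts as abscopal. Protocol 10.3.3 says that, for this study, "abscopal tumor site refers to a lesion that is not irradiated or injected / treated". For Parts 4 and 5, Protocol 8.1.4 says that "the G100 treated site(s) and a non-injected site (unless not available and prior approval is provided by Medical Monitor) must be measurable (Index) lesions".

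Abscopal response is a secondary objective and endpoint (Protocol 5.2 and 5.5, SAP 2.2). The SAP reports abscopal change or response in 5.6.1 (spider and waterfall plots, best percentage change), 5.6.2 (irRC response at abscopal sites and a subgroup), 5.6.4 (a PFS subgroup) and 5.6.8 (a biomarker endpoint). None of these says how to classify a lesion first injected partway through the course.

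**The concern.** Two sites following the same protocol version could treat the same patient differently. One keeps injecting where the lesion was; the other moves to a lesion that had been left alone. The synopsis points to the protocol for detail, but the protocol's own Part 4 design section gives the other instruction.

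What is at stake is mainly the abscopal endpoint. A lesion chosen as a replacement stops being non-injected. If the analysis still carries it as abscopal, shrinkage after direct injection is reported as a distant effect. If it is dropped without a stated rule, the abscopal set depends on the passage each site followed. Either way the change falls on patients whose injected lesion regressed, so it is not random with respect to outcome.

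**Working it through.** **1. Instructions side by side.**

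| Source | Action on regression | Force | Total dose | Non-injected lesions |
|---|---|---|---|---|
| Protocol 6.1 | Inject around the former site | Unconditional | Unchanged | Unchanged |
| Protocol 3.1, SAP 3.1 | Inject another lesion | Unconditional | Unchanged | Can fall |
| Protocol 8.1.4, first statement | Inject another site | Permissive | Unchanged | Can fall |
| Protocol 8.1.4, second statement | Stop | Discretionary; trigger is too small or inaccessible | Reduced | Unchanged |
| Protocol 10.3.18, 10.3.19 | Cancel, only if no peritumoral route and no alternate lesion | Permissive, last resort | Reduced | Unchanged |

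The first two rows are the core conflict: both are unconditional and they name different injection sites. Protocol 6.1 also sits poorly with its own size condition, since a site where a lesion used to be has no tumor of injectable size.

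**2. Total dose.** Inputs: 20 µg per lesion; 1 to 4 lesions by cohort; 6 planned first-course doses (Protocol 6.1). Assumptions: full doses, one-for-one replacement, all target lesions regressing after dose 3, and no optional doses.

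Exposure = 20 µg × lesions × doses.

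| Lesions | Continue to 6 doses (around site or another lesion) | Stop after dose 3 |
|---|---|---|
| 1 | 20 × 1 × 6 = 120 µg | 20 × 1 × 3 = 60 µg |
| 2 | 240 µg | 120 µg |
| 3 | 360 µg | 180 µg |
| 4 | 480 µg | 240 µg |

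The core conflict leaves the total the same. Only stopping changes it, here by half (3/6).

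**3. Abscopal set.** With k non-injected lesions at baseline and r of them used as replacements, k − r remain. Injecting around the site, or stopping, gives r = 0. With k = 1 and r = 1, none remains.

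**4. Scan timing.** Doses 3 to 6 fall on Days 14, 21, 28 and 35. The first scheduled restaging scan is Day 56 ± 7, or Day 63 to 77 if dose 9 is given (Protocol 3.5 and 10.3.20). A replacement lesion first injected by Day 35 therefore has no scheduled post-baseline scan while untreated. Lesions measurable by physical examination are assessed at each visit and may have some earlier measurements.

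**5. Three-dose rules.** Protocol 6.1 (dose-escalation safety evaluability) and Protocol 14.2 (efficacy evaluability) each require at least 3 G100 doses. Dose 3 is due on Day 14. A lesion that regresses after dose 3 has no effect on either rule; they are affected only if dosing stops earlier.

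**6. Design figures.** The Part 4 futility figures reproduce: P(X ≤ 5 | 22, 0.40) = 0.0722 (stated 7.2%) and P(X ≤ 5 | 22, 0.20) = 0.7326 (stated 73.3%). This point does not alter them.

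**The case against.** The best defence is that 10.3.18 and 10.3.19 imply an order: inject in or around the tumor, then use an alternate lesion, then cancel. On that reading 6.1, the permissive statement in 8.1.4 and the stop statement describe successive steps. This has some force, and it makes the stop instruction much the softer part of the conflict. It does not settle the matter. No passage says those visit sections govern, 6.1 has no alternate-lesion step, the synopsis and SAP 3.1 have no peritumoral step, and the stop statement in 8.1.4 does not call for a search for another lesion.

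A second defence is that the definition in 10.3.3 already removes an injected lesion from the abscopal set, and that 8.1.4 requires treated and non-injected index lesions to be recorded. That helps from the injection onward, but the SAP does not say what happens to the lesion's earlier assessments or whether its status is fixed at baseline.

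A third is that SAP 9 records study termination by the sponsor, so rewording site instructions may have little remaining effect. That stands for the protocol text; an SAP rule still matters for any Part 4 abscopal data reported.

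A reader might also infer more than the documents support:

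- **Three equally firm instructions.** The stop statement is discretionary and has a different trigger.
- **A range of 3 to 9 doses.** Doses 7 to 9 require that the tumor has not regressed completely, so 3 versus 6 is the supportable contrast.
- **A general threat to evaluability.** The three-dose rules are affected only by stopping before dose 3, and the Efficacy Evaluable population in SAP 4.3 requires only one injection.
- **A distortion confined to responders.** Regression of an injected lesion is not the same as response, which under Appendix B rests on total tumor burden.

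**Conclusion.** The inconsistency is real and in current text. Its core is Protocol 6.1 against the synopsis and SAP 3.1: two unconditional instructions naming different injection sites, with nothing to say which governs. The consequence is specific: total dose is unchanged, but the set of non-injected lesions can shrink in patients whose injected lesion regressed, and the SAP has no rule for the abscopal summaries that follow. Exposure differs only where a site stops; the halving shown above rests on regression after dose 3, which is an assumed timing.

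The number of affected patients cannot be computed, because the documents give neither the frequency of regression during the course nor the number of non-injected lesions per patient. Part 4's primary endpoints are safety and response frequency, and no sample-size, power or error-rate figure moves. The point is nevertheless more than editorial, because it changes both site conduct and a secondary endpoint.

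**What to change.** - Reconcile Protocol 3.1, 6.1, both statements in 8.1.4, 10.3.18, 10.3.19 and SAP 3.1 to one Part 4 instruction. Which clinical rule applies is for the sponsor to decide; this review takes no position.
- Record the date of first injection for every lesion.
- State in SAP 5.6.1 and 5.6.2 that a lesion first injected mid-course contributes to abscopal summaries only with assessments made before that injection, and carry the rule into the abscopal subgroup in 5.6.4 and the biomarker endpoint in 5.6.8.

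The cost is protocol and SAP wording, one lesion-level flag and slightly fewer abscopal data points. Given the scan schedule, a replacement lesion followed only by imaging and first injected by Day 35 would contribute no scheduled post-baseline abscopal scan, so the number of patients and lesions lost this way should be reported beside the summaries.
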